#### Procedure and discharge related data:

Following the baseline data capture, details on any surgical or endovascular procedure performed, the total duration of hospital admission, the discharge environment or package of care and mobility will be recorded. All patients who agree to participate will be followed up irrespective of whether they undergo any revascularisation.

# Post-operative outcomes:

By review of electronic records 90-days outcome data will be collected. This will include, length of stay (days), death, major adverse limb event (MALE/limb-loss), myocardial and cerebrovascular events (MACE; major adverse cerebrovascular events) and re-admission or re-intervention. Participants will also be invited to receive a telephone call or postal EQ5D assessment for completion. The number of day alive out of hospital will be recorded.

#### Follow-up

Patients will be followed up using electronic patient records. Data as outlined above will be captured. Those patients who agreed to postal or telephone EQ5D assessment will also be assessed at 90 days as well as the Nottingham extended activity of daily living scale where possible. Any patients re-admitted and undergoing repeat CTA imaging within the time frame will also have their skeletal muscle areas re-captured to provide some longitudinal data where possible.

# Sample-size

This study seeks to gather preliminary data to enable future sample size calculations. Although an accurate sample size calculation is not possible without such pilot data, we estimate that a sample size of 200 participants would be sufficient to detect a frailty prevalence of 25% with a precision of +-5% (i.e. 95% CI 20% to 30%). This prevalence is a conservative estimate, based on our local retrospective data for sarcopenia, where the prevalence is approximately 25% of CLTI patients. Frailty rates are estimated to be similar or higher. We aim to recruit a minimum of 40 patients per centre from a minimum of five centres giving a total of 200 patients. So far through national enquiry 10 UK vascular centres have agreed to participation following successful ethical approval. Through our collaborative work we have also been approached by the Fiona Stanley Hospital, Perth, Australia as potential collaborator.

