Sample size	Approximately 30 from each centre of	Approximately 30 from each centre over six months (10 centres)		
Planned study period	9 months (from first recruit)			
	Objectives	Outcome Measures		
Primary	Identify the prevalence of frailty and multi-morbidity among CLTI patients using standardised assessments.	Grip strength assessment and sarcopenia on cross-sectional imaging.		
Secondary	To understand if frailty, multimorbidity and poly pharmacy are associated with adverse clinical outcomes.	1) Major-lower limb amputation rate at 3 months (limb-loss or amputation) 2) Survival at 3 months (who is alive at the three-month timepoint) 3) Re-interventions (repeat surgery or procedures) 4) Length of hospital stay 5) Discharge home 6) Re-admissions and reintervention (who is readmitted to hospital or needs further admission and procedures)		

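### At 25% frailty prevalence, 200 participants give a 95% confidence interval of ±6.0 points rather than the stated ±5, and the per-centre recruitment targets conflict

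*Protocol*

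**What the plan says.** The Aim section makes the prevalence of frailty, sarcopenia and multimorbidity the primary aim. The Sample-size section gives the only numerical justification for the size of the study: "200 participants would be sufficient to detect a frailty prevalence of 25% with a precision of +-5" points, explained as "i.e. 95% CI 20% to 30" per cent. On the choice of 25% it says "This prevalence is a conservative estimate, based on our local retrospective data for sarcopenia", and then "Frailty rates are estimated to be similar or higher".

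On recruitment, the same section says "We aim to recruit a minimum of 40 patients per centre from a minimum of five centres giving a total of 200 patients", and adds that 10 UK centres have agreed to take part. The Sample size row of the study summary table, at the front of the Protocol, reads "Approximately 30 from each centre over six months (10 centres"). It prints no total.

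**The concern.** Prevalence is what the study sets out to estimate, so the width of its confidence interval is the right basis for the sample size. Every input to that calculation is printed in the Protocol, yet the stated interval is narrower than those inputs allow. A study that recruits exactly 200 would follow its Sample-size section and still miss the stated precision, even if the true prevalence were exactly 25%.

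Two further matters bear on the same statement. The expected direction of error in the 25% makes the interval wider, not narrower. And the document does not fix one recruitment target, so it is unclear which size the precision statement should describe. The study is meant to inform later sample size calculations, so its own should be correct.

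**Working it through.** **Inputs, all from the Sample-size section:** n = 200, prevalence p = 0.25, half-width d = 0.05, two-sided confidence 95% (z = 1.96). No allowance for unassessable participants is stated, and none is applied here. Participants are treated as a simple random sample.

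**Step 1. The plan's own figure.** The half-width is z × √(p(1 − p)/n).

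- 1.96 × √(0.25 × 0.75/200) = 1.96 × √0.0009375 = 1.96 × 0.0306 = 0.060.
- The interval is 19.0% to 31.0%, not 20% to 30%.

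**Step 2. Size needed for ±5 points.** n = z² × p(1 − p)/d².

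- 1.96² × 0.1875/0.0025 = 288.1, so 289 participants, about 44% more than 200.

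**Step 3. Can another reading rescue 200?**

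- Other 95% intervals at n = 200 with 25% observed: Wilson 19.5% to 31.4%, Jeffreys 19.4% to 31.3%, Clopper-Pearson 19.2% to 31.6%. None has a half-width of 5 points.
- A 90% two-sided level gives n = 203, and a half-width of 5.04 points at n = 200. This comes close, but the text says 95%.
- A finite population correction would bring 289 down to 200 only for a population of about 650. The Protocol states no such population.
- At 95%, 200 participants give ±5 only if p(1 − p) = 200 × 0.0025/1.96² = 0.130, that is, at a prevalence of about 15.4%. That lies below 25%, the opposite side from where the Protocol expects frailty to be.

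**Step 4. Effect of a higher prevalence.** The product p(1 − p) grows as p approaches 0.5.

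| Prevalence | Half-width, n = 200 | Half-width, n = 300 | n needed for ±5 |
|---|---|---|---|
| 25% | 6.0 | 4.9 | 289 |
| 30% | 6.4 | 5.2 | 323 |
| 40% | 6.8 | 5.5 | 369 |
| 50% | 6.9 | 5.7 | 385 |

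Values above 25% are plausible on the Protocol's own account. The Data collection section expects most participants to receive the walk-speed point automatically, and three points of five denote frailty.

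**Step 5. The two recruitment statements.**

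| Place | Per centre | Centres | Total |
|---|---|---|---|
| Study summary table | about 30 | 10 | none printed; 30 × 10 = 300 |
| Sample-size section | at least 40 | at least 5 | 200, printed; 40 × 5 = 200 |

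A centre that recruits about 30 meets the first statement and fails the second.

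**The case against.** **The study is preliminary.** The Sample-size section says that an accurate calculation is not possible without pilot data. The error is one percentage point in a descriptive study, no test or decision rule depends on it, and the published interval will show the precision achieved. This stands as a comment on size. It does not excuse the figure: the caveat concerns the unknown prevalence, and once 25% is assumed the interval follows by arithmetic.

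**Calling 25% conservative can be fair.** As a low guess at how common frailty is, the word is accurate. A reader might infer that the Protocol is simply wrong to use it, but the text does not support that. What stands is narrower: 25% is not the cautious choice for the precision claim it is used to support. The effect at n = 200 is under one point (6.0 to 6.9).

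**The totals are not strictly incompatible.** A reader might infer that the summary plans 300 and so contradicts 200 outright. The summary prints no total, 300 is only a product of an approximate number and 10, and 200 is built from two minimums. Ten centres at the stated minimum of 40 would even give 400 (±4.2 at 25%). The firm conflict is about 30 against at least 40 per centre, together with different centre counts. Still, the precision claim is made for 200, and 200 is the only total printed.

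**Clustering by centre.** A reader might infer that precision is far worse than ±6.0 because participants come from a few centres. The Protocol gives no intraclass correlation, so any such figure would rest on an assumed one, and the choice of interval may belong to an analysis plan that is not at hand. The point does not rest on it.

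**Conclusion.** The precision statement is wrong as written. At 25% prevalence, 200 participants give a 95% half-width of 6.0 points (19% to 31%); the stated ±5 needs 289, or corresponds to about 90% confidence with 200. No standard 95% interval method closes the gap. If frailty is more common than 25%, as the Protocol expects, the half-width at 200 reaches 6.8 points at 40% and 6.9 at 50%.

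The recruitment statements in the study summary and the Sample-size section also need reconciling, because they differ on participants per centre and on the number of centres. The intended size affects the conclusion: about 300 would meet ±5 at 25% (±4.9) but not at 30% (±5.2) or at 50% (±5.7).

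These figures assume simple random sampling and that every participant has a frailty assessment. The discrepancy is modest in absolute terms. It deserves correction because this is the only stated justification for the size of a study whose primary aim is prevalence.

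**What to change.** 1. In the Sample-size section, restate the precision for 200 participants as ±6.0 points at 25% (95% confidence interval 19% to 31%) and up to ±6.9 points at 50%, and say that this assumes simple random sampling.
2. Do not present 25% as conservative for precision. If the word stays, say that it means a low guess at prevalence.
3. Give one target for participants per centre, number of centres and total, and use it in both the study summary table and the Sample-size section.
4. If the sponsor confirms that 10 centres with about 30 each is the intended target, state about 300 with ±4.9 points at 25% and ±5.7 at 50%, under the same assumption, in place of the figures for 200.

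Keeping 200 costs only wording, and a slightly less favourable stated precision. Confirming about 300 costs more than wording relative to the Sample-size section: 300/200 = 1.5, that is, 50% more recruitment than the total printed there, although the section reports that 10 centres have already agreed to take part.

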# Statistical Analysis

Data were recorded in a dedicated database. Normally distributed data are presented as mean (SD), and hypothesis testing performed with paired and unpaired t-tests. Non-normally distributed data are presented as median (IQR) values with analysis using Mann-Whitney U test for unrelated samples and Wilcoxon signed rank test (WSR) for paired data. Categorical data were analysed by means of chi squared ( $\chi^2$ ) or, if necessary, Fisher's exact test. All data were collected during the dedicated clinic follow-up. Statistical analysis was performed using SPSS version 24 (SPSS, IBM, Chicago, Illinois, USA). A p value of <0.05 was considered statistically significant for single comparisons. Kaplan-Meier survival curves were used with log-rank test to compare the overall mortality. Cox Regression analysis will be performed. Hazards ratios (HR) with 95% confidence intervals (CI's) are reported along with p-values. A HR of greater than 1 indicates a shorter time to death and a HR of less than 1 indicates a longer time-to-death. Binary logistic regression analysis will be used to identify associations with complications and multiple variates will be tested. The resultant significant variables are presented as odds ratios (OR) with 95% CI's. An OR of greater than 1 indicates and increased likelihood of the event occurring.

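### The promised 95% CI of 20% to 30% for frailty prevalence is not what 200 patients from five centres give: ±6.0 points if patients are independent, wider if prevalence varies by centre

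*Protocol*

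**What the plan says.** The primary aim is the prevalence of frailty, sarcopenia and multimorbidity in CLTI (Protocol, Aim). The Background section wants that result to show how large the problem is nationally.

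The Sample-size section says that "a sample size of 200 participants would be sufficient" to "detect a frailty prevalence of 25"% and continues "with a precision of +-5% (i.e. 95% CI 20% to 30"%). It then gives the recruitment structure: "We aim to recruit a minimum of 40 patients per centre from a minimum of five centres giving a total of 200 patients". It mentions neither a design effect nor an ICC, and it describes the study as a source of preliminary data.

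The study summary table gives a different structure: "Approximately 30 from each centre over six months (10 centres"), which is about 300 patients.

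The Statistical Analysis section lists t-tests, rank tests, log-rank, Cox and logistic regression. For categorical data it says "Categorical data were analysed by means of chi squared" or, if needed, Fisher's exact test. Its threshold reads "A p value of <0.05 was considered statistically significant for single comparisons". Centre is not mentioned. The section does not say how the prevalence interval will be calculated and does not name the covariates for the models.

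**The concern.** Patients enter through a small number of centres, 30 to 40 at a time. The precision sentence treats them as a simple random sample of UK patients with CLTI. If frailty prevalence differs between centres, through referral pattern, case mix or the way the score is applied locally, patients from one centre carry overlapping information. An interval computed as if all patients were independent is then too narrow.

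The protocol gives some reason to expect such differences. Recruiters range from trainees to research teams and wider networks. The walk-speed point of the Fried score is given automatically to patients with restricted mobility, while the others take a timed walk.

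The primary result is at stake. The study is also meant to supply the inputs for later sample-size calculations, which would inherit any understated uncertainty.

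**Working it through.** **Inputs from the protocol.** Prevalence p = 0.25, n = 200, target half-width 0.05 and 95% confidence (Sample-size). Structures: 5 centres × 40 = 200 (Sample-size) and 10 centres × about 30 = about 300 (study summary).

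**Assumed input.** The protocol gives no ICC. I use 0, 0.01, 0.02 and 0.05.

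**Step 1: the plan's own figure, with independent patients.**

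- Half-width = 1.96 × √(p(1−p)/n) = 1.96 × √(0.1875/200) = 0.060, so the interval is 19.0% to 31.0%.
- Wilson (19.5% to 31.4%) and Clopper-Pearson (19.2% to 31.6%) intervals do not rescue it.
- n for ±5 points = 1.96² × 0.1875 / 0.05² = 288.1, so 289 patients.
- A 90% interval at n = 200 would give ±5.04 points, but the text says 95%.
- At n = 300 the half-width is 1.96 × √(0.1875/300) = 0.049.

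The stated ±5 points is therefore not reproduced at 200. It would be met at 300, but only under independence.

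**Step 2: allow for centre.** With m patients per centre:

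- design effect DE = 1 + (m−1) × ICC
- half-width = 1.96 × √(p(1−p)/n) × √DE
- coverage of an interval that ignores centre = 2Φ(1.96/√DE) − 1
- n for ±5 points = 288.1 × DE, rounded up

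Example, 5 × 40 at ICC 0.02: DE = 1 + 39 × 0.02 = 1.78; √DE = 1.334; half-width = 6.0 × 1.334 = 8.0 points; coverage = 2Φ(1.469) − 1 = 0.858.

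| 5 centres × 40 | ICC 0 | 0.01 | 0.02 | 0.05 |
|---|---|---|---|---|
| Design effect | 1 | 1.39 | 1.78 | 2.95 |
| Effective n | 200 | 144 | 112 | 68 |
| Half-width, 1.96 (points) | 6.0 | 7.1 | 8.0 | 10.3 |
| Half-width, t on 4 df (points) | 8.5 | 10.0 | 11.3 | 14.6 |
| Coverage if centre is ignored | 95% | 90% | 86% | 75% |
| n for ±5 points | 289 | 401 | 513 | 850 |

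| 10 centres × 30 | ICC 0 | 0.01 | 0.02 | 0.05 |
|---|---|---|---|---|
| Design effect | 1 | 1.29 | 1.58 | 2.45 |
| Effective n | 300 | 233 | 190 | 122 |
| Half-width, 1.96 (points) | 4.9 | 5.6 | 6.2 | 7.7 |
| Half-width, t on 9 df (points) | 5.7 | 6.4 | 7.1 | 8.9 |
| Coverage if centre is ignored | 95% | 92% | 88% | 79% |
| n for ±5 points | 289 | 372 | 456 | 706 |

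**Step 3: separate the two sources of error.** For 5 × 40, one point of the gap from ±5 is plain arithmetic (6.0 − 5.0). Clustering adds 1.1 / 2.0 / 4.3 points to that at ICC 0.01 / 0.02 / 0.05. For 10 × 30, clustering adds 0.7 / 1.3 / 2.8 points to a baseline of 4.9.

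**Step 4: the association analyses.** Frailty is measured on each patient and varies within centres. An approximation for such a contrast is 1 + (m−1) × ICC of exposure × ICC of outcome. With both ICCs at 0.01 / 0.02 / 0.05 and m = 40 this is 1.004 / 1.016 / 1.10. Standard errors then change by about 0.2% / 0.8% / 5%, far less than the table for the prevalence would suggest.

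**The case against.** **The size depends on an assumption.** The protocol gives no ICC, and at ICC 0 there is no clustering loss. This stands: the figures in step 2 are conditional, and zero has to be part of the stated range. It does not touch step 1, which needs no assumption about clustering.

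**The structure is not fixed, and the study is preliminary.** Forty patients and five centres are minimums, and the section itself says an accurate calculation is not possible without pilot data. That is fair. But the 20% to 30% interval is attached to 200 patients, and 200 patients do not give it. More centres with the same total would help: 10 × 20 gives ±6.6 / 7.1 / 8.4 points at ICC 0.01 / 0.02 / 0.05, which is still wider than ±5.

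**Handling of centre can be left to the SAP.** For the regression models this stands. The protocol neither plans nor excludes a centre term, and its silence is not an error. The precision claim is different, because the protocol itself states it.

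**A stronger reading.** A reader might infer from the list of tests that the chi-squared, log-rank, Cox and logistic p-values will all be too optimistic. The protocol does not support that. Because frailty varies within centres, the design effect for a prevalence does not apply, and ignoring centre could make those tests anti-conservative, neutral or conservative. What remains is possible confounding by centre, for example if amputation, length of stay or discharge home depends on local practice. The protocol gives no figure for that.

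**Conclusion.** The point holds for the primary prevalence interval and its sample-size justification. The stated 95% CI of 20% to 30% at 200 patients is wrong even with independent patients (±6.0 points; 289 needed for ±5), and it leaves no room for variation between centres. For any positive ICC, a simple binomial interval for the multicentre prevalence would be too narrow. With 1.96 and an assumed ICC of 0.01 to 0.05, the half-width is ±7.1 to ±10.3 points for 5 × 40 and ±5.6 to ±7.7 for 10 × 30.

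This rests on the assumed ICC range, equal centre sizes, a prevalence of 25%, and a target population wider than the participating centres, as the national aim in the Background implies. The Statistical Analysis section does not say that a simple binomial interval will be used, so the coverage figures describe what would follow if it were. No conclusion is drawn about the p-values of the association analyses.

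**What to change.** In the Sample-size section:

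- replace ±5 points at 200 with the correct independence figure (±6.0 points, or 289 patients for ±5);
- reconcile the 200 given there with the roughly 300 in the study summary table;
- give the expected half-width for the chosen structure over a stated ICC range that includes zero.

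In the Statistical Analysis section, say that the primary prevalence interval will use a centre-clustered variance with a t reference on centres minus one degrees of freedom. Acknowledge that this is imprecise with 5 to 10 centres: with five, the t reference alone takes ±6.0 to ±8.5 points at ICC 0.

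For the association analyses, adjusting for or stratifying by centre is a sensible guard against confounding. It can be specified in the SAP.

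The cost is wording and a wider, less favourable stated interval. No new data should be needed: centre is not in the listed baseline items, but it should be known because recruitment is by site. If the sponsor wants to keep ±5 points, the cost is more patients or more centres.

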It is postulated that CLTI patients with frailty and/or multi-morbidity, may be associated with worse outcomes, potentially independent of age. FraiLTI has been developed to assess the nationwide scale of the problem and to develop a platform on which to build future intervention studies to mitigate the impact of frailty, sarcopenia and multimorbidity in this group of patients

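### The logistic analysis of complications presents odds ratios by significance, which exaggerates them and leaves null associations unreported, and nothing in the text keeps age in the model

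*Protocol*

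**What the plan says.** The Statistical Analysis section of the protocol assigns binary logistic regression to associations with complications. It then states that "multiple variates will be tested. The resultant significant variables are presented as odds ratios (OR) with 95% CI's". It names no covariates and describes no other logistic output. The only significance level in the section is "A p value of <0.05 was considered statistically significant for single comparisons". In the same section, mortality is analysed by Kaplan-Meier, log-rank and Cox methods. Hazard ratios there are reported with intervals and p-values, with no condition that they be significant.

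The Background postulates that frailty and/or multimorbidity "may be associated with worse outcomes, potentially independent of age". The secondary aim is to find associations with clinical outcomes that will support risk prediction and modelling. The Sample-size section describes the study as preliminary data for later sample size calculations.

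The planned size is "giving a total of 200 patients" in the Sample-size section. The study summary table gives "Approximately 30 from each centre over six months (10 centres"), which is about 300. Both sizes are used below.

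**The concern.** If an odds ratio is presented because it was significant, the presented values are a selected sample. In a small study only large estimates reach p < 0.05, so those shown overstate the true effect on average, and their 95% intervals take no account of the selection. An exposure with no clear association is not shown at all, although that result also answers the secondary aim.

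This matters more here than in a purely descriptive report, because the size of the effect is what later work will use. A study sized on an exaggerated odds ratio will be too small, and a risk model built on such values will be too confident.

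Age is the obvious confounder of frailty, and the protocol's own hypothesis refers to it. Because no covariate is fixed, an analyst could follow the text to the letter and report a frailty odds ratio that is not adjusted for age.

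**Working it through.** **The plan's own figure.** The logistic analysis has none: no event rate, odds ratio or power is stated. The only sample-size figure is for prevalence, to "detect a frailty prevalence of 25% with a precision of +-5" percentage points with 200 patients. That gives 1.96 × √(0.25 × 0.75 / 200) = 0.060, or ±6.0 points. This is a separate matter and does not affect the present point.

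**Inputs from the protocol.** N = 200 or 300. Frailty 25%, with 50% as a second value because "Frailty rates are estimated to be similar or higher". Two-sided p < 0.05, taken as the filter because no other level is given.

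**Assumptions, not in the protocol.** True odds ratio 1.8. Event risk in the non-frail 8% or 25%.

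**Step 1: how large an estimate must be to pass.** The standard error of the log odds ratio is √(1/a + 1/b + 1/c + 1/d), using expected cell counts.
- N = 200, 25% frail, 8% events. Odds in the frail are 1.8 × 0.08/0.92 = 0.1565, so the risk is 13.5%. Cells are 6.77, 43.23, 12 and 138. SE = √0.2615 = 0.511, and the threshold is exp(1.96 × 0.511) = 2.72, well above the true 1.8.
- N = 300, 50% frail, 25% events. The risk in the frail is 37.5%. Cells are 56.25, 93.75, 37.5 and 112.5. SE = √0.0640 = 0.253, and the threshold is exp(1.96 × 0.253) = 1.64, just below the true 1.8.

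**Step 2: what is presented on average.** I simulated 400,000 two-by-two tables per row with a Wald test on the log odds ratio. The presented value is the geometric mean among runs with p < 0.05. Runs with an empty cell, fewer than 0.1%, were left out.

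| N | Frail | Events in non-frail | Expected events | Significant | Presented OR | Median OR, no filter |
|---|---|---|---|---|---|---|
| 200 | 25% | 8% | 18.8 | 21% | 3.59 | 1.74 |
| 200 | 50% | 8% | 21.5 | 22% | 3.65 | 1.81 |
| 200 | 25% | 25% | 56.2 | 40% | 2.53 | 1.81 |
| 200 | 50% | 25% | 62.5 | 48% | 2.36 | 1.80 |
| 300 | 25% | 8% | 28.2 | 30% | 2.89 | 1.78 |
| 300 | 50% | 8% | 32.3 | 33% | 2.86 | 1.81 |
| 300 | 25% | 25% | 84.4 | 54% | 2.22 | 1.80 |
| 300 | 50% | 25% | 93.8 | 65% | 2.09 | 1.81 |

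**Step 3: other true effects** (25% frail). With a true odds ratio of 1.5, N = 200 and 10% to 20% events, 14% to 20% of runs are significant and the median presented value is 3.07 to 2.45. The smallest harmful estimate that passed was about 1.96, so a true 1.5 can be presented as harmful only if overstated. With a true odds ratio of 2.5, N = 300 and 20% events, the median presented value is 2.61, and the bias is nearly gone.

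**Step 4: consequence for a later sample size.** Required size varies roughly with 1/(ln OR)², if the variance per patient is held fixed. Planning on 3.59 when the truth is 1.8 gives (0.588/1.278)² = 0.21 of the size needed. Planning on 2.09 gives (0.588/0.737)² = 0.64.

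**Step 5: age.** Assume an age odds ratio of 1.4 per SD, age-related frailty at 25% and overall event rates of 10% to 20% (1,000 simulated studies per scenario). In a model with frailty and age, age is non-significant in 57% to 74% of runs at N = 200 and in 41% to 64% at N = 300. At N = 200 with no true frailty effect, the median frailty odds ratio is 1.20 to 1.22 without age and 0.96 to 1.00 with it.

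**The case against.** The strongest reply is that the sentence concerns presentation, not model building. It states no stepwise removal and no p-value for entry. Fitting all variates together, age included, and then showing the significant ones fits the same words and does adjust for age. This stands. A reader might infer that age stays in the model only if it is significant, but the protocol does not say so. What can be said is that nothing keeps age there. The age hypothesis is itself hedged. That only significant results are shown is also an inference, though the natural one: the wording ties presentation to the test, and no other logistic results are promised.

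A reader might also infer that null findings vanish from the whole study. They do not. The filter covers the logistic analysis of complications, and the Cox results for mortality are reported without it.

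A doubled odds ratio is tempting as a headline, but it is the unfavourable end of an assumed range. Readmission and reintervention may be common, and frailty may exceed 25%. Both reduce the bias.

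One might cross every exposure with every outcome and quote a false-positive rate. The protocol sets out no such grid, and length of stay and survival are not binary logistic outcomes, so no such rate is given here. Handling of centre, penalised estimation, multiplicity and the choice of a main association may be left to an analysis plan and form no part of this point.

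**Conclusion.** The concern holds for the logistic analysis of complications. The rule written in the protocol, followed as it stands, exaggerates the odds ratios it presents and leaves null associations unpresented. An analysis plan that obeyed the sentence would inherit the fault. The direction was the same in every scenario run. The size rests on assumed event rates and effects: for a true odds ratio of 1.8, about 3.6 down to 2.4 with 200 patients and 2.9 down to 2.1 with 300, against about 1.8 unfiltered. The bias becomes small when the true effect is large and events are many.

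The text also leaves the age-independent hypothesis unprotected, because it does not fix age in the model. The primary prevalence aim and the survival analysis are unaffected. The sentence should be changed, because the secondary aim and the planned later use of the estimates depend on it.

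**What to change.** Replace the sentence on presenting significant variables with one to this effect: for each binary complication outcome, the odds ratio and 95% confidence interval for frailty, sarcopenia and multimorbidity will be reported whatever the p-value; age will be kept in each model whatever its p-value; these associations are exploratory.

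This changes wording only and needs no new data, visits or patients. The cost is that fewer results will be highlighted as significant, and some reported intervals will look wide.

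In the unfiltered runs above, reporting every estimate brings the median odds ratio back to 1.74 to 1.81 for a true 1.8. Keeping age in the model brings the frailty odds ratio back to about 1 when frailty has no effect of its own.
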